8.4.2 Unified Parkinson's Disease Rating Scale (UPDRS)

The UPDRS is an Investigator-used rating tool to follow the longitudinal course of PD. It is made up of the following sections: I) Mentation, Behavior, and Mood; II) Activities of Daily Living; III) Motor Examinations; IV) Complications of Therapy sections (including Dyskinesias); and V) Modified Hoehn and Yahr Staging, as well as the Schwab and

England Activities Of Daily Living Scale. These are evaluated by physical examination and observation. Some sections require multiple grades assigned to each extremity.

- The Part I sub-score is the sum of the answers to the 4 questions that comprise Part I, each of which are measured on a 5-point scale (0 – 4). The Part I score will range from 0 – 16. No missing answers will be imputed so the Part I score will be missing if any of the answers are missing.
- The Part II sub-score is the sum of the answers to the 13 questions that comprise Part II, each of which are measured on a 5-point scale (0 – 4). The Part II score will range from 0 – 52. The UPDRS Part II score will be calculated as long as at least 12 questions have been answered. If 1 answer is missing the Part II score will be calculated by multiplying the sum of questions answered by the ratio of the total number of Part II questions to the number of questions answered.
- UPDRS Part III consists of 14 questions. Questions 20 – 26 are multi-part questions in that they are evaluated separately for multiple body parts. For example, Question 24, related to hand movements, is assessed separately for the left and right hand. Counting each of these assessments leads to a total of 27 answers for Part III. The Part III sub-score is the sum of the 27 answers provided to the 14 Part III questions, each of which is measured on a 5-point scale (0 – 4). The Part III score will range from 0 – 108. The UPDRS Part III score will be calculated as long as at least 23 answers have been recorded. If 4 or fewer answers are missing the Part II score will be calculated by multiplying the sum of the answers provided by the ratio of the total number of Part III answers possible (27) to the number of answers provided.
- The total score is the sum of the responses to the 31 questions (44 answers) that comprise Parts I – III of the scale. The total score ranges from 0 – 176 with 176 representing the worst (total) disability, and 0 no disability. The UPDRS Total score will be calculated as long as 38 answers have been recorded. If 6 or fewer answers are missing the Total score will be calculated by multiplying the sum of answers provided by the ratio of the total number of answers possible (44) to the number of answers provided.
- The Part IV Score is the sum of the answers to the 11 questions that comprise Part IV, 4 of which are measured on a 5-point scale (0 – 4) and 7 which are

measured on a 2-point scale (0 – 1). The Part IV score will range from 0 – 23. The UPDRS Part IV score will be calculated as long as at least 10 questions have been answered. If 1 answer (i.e., < 15%) is missing the Part IV score will be calculated by multiplying the sum of questions answered by the ratio of the total number of Part IV questions to the number of questions answered.

- Additionally, Questions 32, 33, and 34 on UPDRS Part IV will be totaled to evaluate dyskinesias. Each of these questions is measured on a 5-point scale (0 – 4). The Part IV dyskinesia score ranges from 0 – 12. No missing answers will be imputed so the Part IV score will be missing if any of the answers are missing.

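### SAP 8.4.2 prorates UPDRS Part IV by item count although its items have different maxima, so the rule does not preserve the stated 0–23 range

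*SAP*

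**What the plan says.** SAP 8.4.2 defines the score in these words: "The Part IV Score is the sum of the answers to the 11 questions that comprise Part IV". Four of the items are scored 0–4 and seven are scored 0–1. The stated range is "The Part IV score will range from 0 – 23".

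One missing answer is tolerated: "The UPDRS Part IV score will be calculated as long as at least 10 questions have been answered". The score is then obtained by "multiplying the sum of questions answered by the ratio of the total number of Part IV questions to the number of questions answered". The section has no cap, no rounding rule and no weighting by item maximum.

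The next bullet defines the dyskinesia score from Questions 32 to 34 (range 0–12) and ends: "No missing answers will be imputed so the Part IV score will be missing if any of the answers are missing".

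The same section handles the other parts as follows:

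- **Parts II, III and the Total** are prorated by item count, but all their items share one maximum. For Part II the wording is "each of which are measured on a 5-point scale (0 – 4). The Part II score will range from 0 – 52".
- **Part I** is not imputed at all.

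For the PDQ-39 summary index (SAP 8.4.4), the sum is divided by the highest attainable score, and that score is reduced when answers are missing.

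Change in Part IV is a listed efficacy variable (protocol 13.3; SAP 9.9, table 14.2__2.2.5). It is reported with confidence intervals and within-group tests, for the US subset only.

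**The concern.** Proration by item count is neutral for the range only when every item has the same maximum. Part IV is the only prorated UPDRS score for which this fails, so the rule may have been carried over from Parts II and III.

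Two things follow. A prorated value can fall outside the range that the same bullet states. And the size and sign of the error for a subject depend on which item happens to be blank. The endpoint is a single value, the last non-missing one in the treatment period (SAP 6.4.6), so an error at that visit passes undiluted into the subject's change score.

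The last sentence of the dyskinesia bullet adds a literal contradiction. One bullet calculates Part IV with 10 of 11 answers, and the next says that Part IV is missing if any answer is missing. A programmer cannot implement both.

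**Working it through.** **Inputs (all SAP 8.4.2).** 11 items: 4 with maximum 4, and 7 with maximum 1. At most one answer may be missing. Let S be the sum of the 10 answered items and m the maximum of the missing item. The prorated score is S × 11/10.

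**1. The plan's own range.** Complete data: 4 × 4 + 7 × 1 = 16 + 7 = 23. The stated 0–23 reproduces.

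**2. Largest prorated score.**

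- 0–1 item missing: S is at most 22, and 22 × 1.1 = 24.2, above 23.
- 0–4 item missing: S is at most 19, and 19 × 1.1 = 20.9, so 23 cannot be reached.

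**3. How often 23 is exceeded.** With a 0–1 item missing, only S = 21 (23.1) and S = 22 (24.2) exceed 23. There are 5⁴ × 2⁶ = 625 × 64 = 40,000 answer patterns for the 10 answered items. One gives S = 22. Ten give S = 21: four with one 0–4 item at 3, and six with one 0–1 item at 0. That is 11 of 40,000, all near-maximal. This counts patterns and is not a probability.

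**4. Value implied for the missing item.** S × 1.1 − S = S/10. For a 0–1 item this exceeds 1 whenever S > 10 and can reach 2.2. For a 0–4 item it never exceeds 1.9. The rule therefore misbehaves at mid-scale too, not only at the top.

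**5. Error under proportional severity.** Assume that the subject is at the same fraction of maximum on every item.

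- 0–1 item missing: 24.2/23 − 1 = +5.2%.
- 0–4 item missing: 20.9/23 − 1 = −9.1%.

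At half of maximum (true score 11.5), the rule gives 11 × 1.1 = 12.10 or 9.5 × 1.1 = 10.45.

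**6. Group mean.** Let T be the full score. If each of the 11 items is equally likely to be missing, independent of its value, the expected observed sum is T − T/11, and 1.1 × (T − T/11) = T. The errors cancel.

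**7. Proration by attainable score.** S × 23/(23 − m) gives 22 × 23/22 = 23 and 19 × 23/19 = 23, so the range holds. The implied item value is S × m/(23 − m), at most 1 for a 0–1 item and at most 4 for a 0–4 item.

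**8. Two assumed profiles.** Profile A averages 2 on the 0–4 items and 0.4 on the 0–1 items (true 8 + 2.8 = 10.8). Profile B averages 1 and 0.7 (true 4 + 4.9 = 8.9).

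| Profile, missing item | S | SAP rule (error) | Attainable-score rule (error) |
|---|---|---|---|
| A, 0–4 item | 8.8 | 9.68 (−1.12) | 10.65 (−0.15) |
| A, 0–1 item | 10.4 | 11.44 (+0.64) | 10.87 (+0.07) |
| B, 0–4 item | 7.9 | 8.69 (−0.21) | 9.56 (+0.66) |
| B, 0–1 item | 8.2 | 9.02 (+0.12) | 8.57 (−0.33) |

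Weighting profile A by item numbers, the SAP rule averages (4 × 9.68 + 7 × 11.44)/11 = 10.8, the true score, as step 6 predicts.

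**The case against.** The strongest reply is that no bias in the reported result has been shown. That stands. A reader might infer that the Part IV mean change is biased. The documents do not support this: with equal, value-independent missingness across the 11 items the count rule is exactly right on average (step 6), and neither document reports which items go missing or how often.

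A second tempting inference is that proration by attainable score is simply more accurate. It is not. Profile A suits it because the subject is at similar fractions of maximum on both item types (50% and 40%). In profile B (25% and 70%) the SAP rule is closer in both cases. The alternative guarantees the range, not a smaller error for every subject.

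Third, values above 23 will be rare, and little rests on them. The protocol has no primary outcome measure (11.5) and no alpha level (13.4). The UPDRS Total (Parts I–III) and the dyskinesia score do not use this rule.

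Fourth, the dyskinesia bullet is a slip whose meaning is clear from context, since the preceding sentence names the dyskinesia score. That is fair, and the correction is editorial.

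None of this makes the rule consistent with its own stated range. Nothing elsewhere in the SAP caps the score.

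**Conclusion.** The Part IV proration rule is wrong as written: it does not preserve the range that the same bullet states. The ceiling is 24.2 with a 0–1 item missing and 20.9 with a 0–4 item missing. For a 0–1 item the implied answer is impossible whenever the observed sum exceeds 10. These results need only the item structure in SAP 8.4.2.

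The figures of about +5% and −9% rest on the assumption of proportional severity and describe a score with a given item missing, not the group mean. A net effect on the mean needs unequal or value-dependent item missingness and cannot be sized from the documents.

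The reach is narrow: Part IV scores with exactly one missing answer, in the US subset. This is a minor point, worth correcting because it costs little, and it does not threaten the study's conclusions.

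**What to change.** In SAP 8.4.2, replace the Part IV proration with one of these:

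- **By attainable score:** sum of answers × 23/(23 − maximum of the missing item). The factor is 23/22 for a 0–1 item and 23/19 for a 0–4 item. This follows the principle already used for the PDQ-39 summary index.
- **No imputation,** as for Part I. This also removes the range problem. The price is that a visit with one blank item yields no Part IV score, so the endpoint falls back to an earlier visit or is lost.

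Apply the chosen rule to every value that enters a change score. SAP 6.4.4 and 6.4.5 take the initial-infusion and 3005 baseline values from earlier study databases, and the SAP does not say whether item answers or derived scores are retrieved. If derived scores are used, changing only the 3005 formula could mix two scoring rules within one change score. Confirm this, and rescore from item answers where they are available.

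Reword the last sentence of the dyskinesia bullet so that the Part IV dyskinesia score (Questions 32–34), not the Part IV score, is set to missing when any of its three answers is missing.

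The cost is one formula, a short wording correction, and a check of how the earlier Part IV values were derived.

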8.4.3 Clinical Global Impression – Improvement (CGI-I)

The CGI-I is a global assessment by the Investigator of the change in clinical status since the start of treatment. The CGI-I ratings are as follows:

- 1 = very much improved
- 2 = much improved
- 3 = minimally improved
- 4 = no change
- 5 = minimally worse
- 6 = much worse
- 7 = very much worse

8.4.4 Parkinson's Disease Questionnaire (PDQ-39)

The PDQ-39 is a disease-specific, instrument designed to measure aspects of health that are relevant to subjects with PD, and which may not be included in general health status questionnaires. The PDQ-39 is a self-administered questionnaire that comprises 39 items addressing the following eight domains of health that subjects consider to be adversely affected by the disease:

- Mobility (e.g., fear of falling when walking) – 10 questions

- Activities of daily living (e.g., difficulty cutting food) – 6 questions
- Emotional well-being (e.g., feelings of isolation) – 6 questions
- Stigma (e.g., social embarrassment) – 4 questions
- Social support – 3 questions
- Cognition – 4 questions
- Communication – 3 questions
- Bodily discomfort – 3 questions

Each question is answered on the following 5-point scale: 0 = Never, 1 = Occasionally, 2 = Sometimes, 3 = Often, 4 = Always or Cannot Do At All. The PDQ-39 is scored on a scale of 0 to 100, where lower scores indicate a better perceived health status. Higher scores are consistently associated with the more severe symptoms of the disease such as tremor and stiffness. The domain scores are calculated by first summing the answers to the questions in the domain. The sum is divided by the highest score possible (i.e., number of question multiplied by 4) and the quotient is multiplied by 100 to put the score on a scale from 0 to 100. The Social Support domain has 1 question that cannot be answered if the subject does not have a spouse or partner. If the subject does not have a spouse or partner, the domain score is calculated as if the domain only had two questions. The PDQ-39 summary index (PDQ-39SI) is the sum of all answers divided by the highest score possible (i.e., number of answers multiplied by 4) which is multiplied by 100 to put the score on a 0 to 100 scale. The domain scores will only be calculated if all of the questions are answered. The PDQ-39SI will be calculated as long as no more than 15% (5) of the answers are missing. This enables calculation of the PDQ-39SI even if one or more of the domain scores are not calculated. The highest score possible will be adjusted based on the number of answers provided.

8.5 Safety Analysis Variables

8.5.1 Adverse Events

Adverse event (AE) Investigator terms are assigned to a Lowest Level Term (LLT) and a Preferred Term (PT) and will be classified by High Level Term (HLT), High Level Group

Term (HLGT) to one System Organ Class (SOC), namely the primary SOC, according to the MedDRA thesaurus, Version 14.0.

AE Investigator terms that are related to procedural or device complications may also have a secondary coding. For example, consider the verbatim term "Worsening of Parkinson's disease due to PEG-J dislocation." This AE can be coded as follows:

Primary Coding –

- Lower Level Term: 'PARKINSONISM AGGRAVATED'
- Preferred Term: 'PARKINSONISM'
- System Organ Class: 'NERVOUS SYSTEM DISORDERS'

Secondary Coding –

- Lower Level Term: 'DEVICE DISLOCATION'
- Preferred Term: 'DEVICE DISLOCATION'
- System Organ Class: 'INJURY, POISONING AND PROCEDURAL COMPLICATIONS'

AE summaries will include the primary as well as the secondary coding.

A detailed description of each AE includes:

- The start and stop date of the event or "Ongoing" at the end of the study.
- Severity (categorized as "Mild," "Moderate" or "Severe"). If severity is missing it will be regarded as "Severe."
- Relationship to the investigational therapeutic system (categorized as "Unrelated," "Unlikely," "Possible" or "Probable").
- Action taken with investigational study medication:
 - Drug discontinued.
 - Drug interrupted.
 - Dosage reduced.

- Dosage increased.
- None/not applicable.
- Outcome of event, which is defined as any one of the following:
 - Recovered/Resolved.
 - Recovered/Resolved with Sequelae.
 - Fatal.
 - Unknown.

If an adverse event is "Ongoing," the Outcome will be blank.

- Serious, categorized as "Yes" or "No."
- Concomitant treatment/therapy introduced, categorized as "Yes" or "No."
- Led to study termination, categorized as "Yes" or "No."

Missing and/or incomplete dates for AEs are imputed in a manner resulting in the earliest onset within the Treatment Period and the longest duration. However, the Stop Date will not be imputed if the event is reported as "Ongoing."

Technically, this will be done as follows:

For a missing/incomplete start date the minimum of the following will be imputed:

- The maximum of the earliest possible start date and the date of first administration of investigational study drug
- The latest possible start date
- The latest possible stop date

For a missing/incomplete stop date the maximum of the following will be imputed:

- The minimum of the latest possible stop date and the date of last administration of investigational study drug
- The earliest possible stop date
- The earliest possible start date

Here, the earliest (latest) possible date is defined as:

- The date itself if it is possible
- The date of the first (last) day of the month, if month and year are available but the day is missing
- The date of the first (last) day of the year, if year is available but day and month are missing
- A very early (late) date, for example, 01JAN1000 (01JAN3000), if the date is completely missing

From this data the following will be determined and used for presentation in the applicable tables and listings:

- Treatment-Emergent Adverse Events (TEAEs): Defined as AEs which started on or after the Date of the First 3005 LCIG Infusion and within 30 days of the Date of the Last 3005 PEG-J Exposure.
- Treatment-Emergent Serious Adverse Events (TESAEs): Defined as TEAEs regarded by the Investigator as Serious.
- TEAEs that are at least possibly related to the therapeutic system: Defined as TEAEs assessed as having a "Possible" or "Probable" relationship to the investigational therapeutic system and includes those events where the relationship is missing.
- Severe TEAEs: Defined as TEAEs assessed as being "Severe" in intensity and includes those events where the severity is missing.
- TEAEs that led to premature discontinuation: Selected as those events where: "Led to Study Termination" is indicated as "Yes."
- TEAEs with fatal outcome as reported on the "Adverse events" CRF.
- TEAEs in the following categories have been defined as TEAEs of special interest:
 - Procedure and device associated events
 - Polyneuropathy (broad search as well as narrow search)
 - Weight loss

- Cardiovascular fatalities
- Respiratory tract aspiration including aspiration pneumonia/pneumonitis

TEAEs are included in a category of special interest based on their PT and, in the case of cardiovascular fatalities, their outcome. The list of PT's assigned to each category is included as Appendix 12.4. Only TEAEs where an outcome of "Fatal" has been reported on the "Adverse Event" CRF are to be included in the category of cardiovascular fatalities. All events with PT's other than those assigned to the procedure and device associated AESI category will be included in summaries of events that are not procedure and device related.

The percentage of each of the aforementioned AE types will be determined as the number of subjects with at least one mention of the AE type relative to the number of subjects at risk. A subject will be considered at risk if the subject is in the Safety subject sample.

In addition to the aforementioned AE types, AEs reported by the Investigator as related to device complications will also be summarized. Device complications are captured in the DE raw data panel and associated AEs are captured in the AE raw data panel.

Investigators link the AEs that are related to device complications by entering an AE number in the DE raw data panel.

The incidence and prevalence of TEAEs during each 3005 Treatment Year will be summarized using the study day intervals described in Section 6.4.9. AE start days and Treatment Period end days will be calculated relative to the start of 3005 LCIG infusion (RFSTDTN) as follows:

$$\text{AE Start Day} = (\text{AE Start Date} - \text{Date of First 3005 LCIG Infusion}) + 1$$

$$\text{Treatment Period End Day} = ([\text{Date of Last 3005 PEG-J Exposure} + 30 \text{ Days}] - \text{First Date of 3005 LCIG Infusion}) + 1$$

For summaries of incidence, the count (and numerator for percentage calculations) will be the number of subjects who had their first treatment-emergent occurrence of the PT start

within the study day range for the 3005 Treatment Year. Each subject will be counted at most once within each SOC and PT.

For summaries of prevalence, the count (and numerator for percentage calculations) will be the number of subjects who had a treatment-emergent occurrence of the PT start within the study day range for the 3005 Treatment Year or who had an earlier treatment-emergent occurrence of the PT that had not ended prior to the start of the study day range for the 3005 Treatment Year.

The denominator for both incidence and prevalence percentage calculations will include all subjects whose Treatment Period End Day is within or greater than the study day range for the 3005 Treatment Year.

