6.4.6 Treatment Period

Data collected on the Date of the First 3005 LCIG Infusion (Day 1) will be assigned to the Baseline Period. However, adverse events and concomitant medications starting on Day 1 will be assigned to the Treatment Period (worst case scenario).

A Gap Period (number of days) is defined to include data collected after the end of the relevant Treatment Period in the analysis. For this study, the Gap Period will be 30 days for adverse events and 1 day for all other assessments.

For efficacy assessments the Treatment Period is defined as the Period from the Date of the First 3005 LCIG Infusion up to and including the Date of the Last 3005 LCIG Infusion + Gap Period (1 day). For safety assessments the Treatment Period is defined as the Period from the Date of the First 3005 LCIG Infusion up to and including the Date of the Last 3005 PEG-J Exposure + Gap Period (30 days for adverse events and 1 day for all other assessments).

The Endpoint value for a variable is defined as the last non-missing value assigned to the Treatment Period for the subject.

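### The SAP caps imputed AE stop dates at the last study-drug date although the AE period runs to last PEG-J exposure + 30 days, so some events at the end of treatment are cut short and by-year prevalence can be understated

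*SAP*

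**What the plan says.** SAP 8.5.1 states the aim of the imputation: "Missing and/or incomplete dates for AEs are imputed in a manner resulting in the earliest onset within the Treatment Period and the longest duration". Stop dates of events reported as ongoing are not imputed.

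The stop-date rule reads "For a missing/incomplete stop date the maximum of the following will be imputed", followed by three candidates:

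1. "The minimum of the latest possible stop date and the date of last administration of investigational study drug"
2. "The earliest possible stop date"
3. "The earliest possible start date"

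A date with a missing day is bounded by the first and last day of the month. A date with only the year is bounded by the first and last day of that year. A wholly missing date is bounded by 01JAN1000 and 01JAN3000.

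SAP 6.4.6 ends the safety Treatment Period at "Date of the Last 3005 PEG-J Exposure + Gap Period (30 days for adverse events and 1 day for all other assessments"). The TEAE definition in 8.5.1 uses the same 30 days after last PEG-J exposure. Under 6.4.1, last PEG-J exposure (RFENDT2N) is never earlier than the last infusion (RFENDTN), and it is later when removal of the PEG-J is recorded after the last infusion.

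For by-year prevalence, 8.5.1 counts a subject with an onset in the year, or one "who had an earlier treatment-emergent occurrence of the PT that had not ended prior to the start of the study day range". The denominator is every subject whose Treatment Period End Day, which is last PEG-J exposure + 30 days, reaches that year.

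**The concern.** The upper bound in the stop-date rule is not the end of the period in which AEs are counted. For a subject who has left treatment it is at least 30 days too early. The start-date rule has no such problem, because its bound, the first administration, is where the Treatment Period begins. SAP 10.1, on changes to planned analyses, does not mention the difference.

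The rule therefore cannot deliver its stated property for events whose stop date could lie after the last dose. This is the interval that contains PEG-J removal and the 30 days of AE reporting after it. In the prevalence tables, such an event can be treated as over before a Treatment Year starts while the subject is still in that year's denominator.

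**Working it through.** The plan gives no figure to reproduce, so the check applies the rule as written:

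stop = max{ min(latest possible stop, last dose), earliest possible stop, earliest possible start }.

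**Durations.** Assumed dates: last dose 20 Mar 2014, PEG-J removal 3 Apr, so the AE period ends 3 Apr + 30 days = 3 May. For onset 28 Mar with the stop date missing: min(01JAN3000, 20 Mar) = 20 Mar; earliest stop 01JAN1000; earliest start 28 Mar; the maximum is 28 Mar, a 1-day event. The same steps for 11 events give, in days:

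| Onset | Recorded stop | Imputed stop | Duration | Shortest | Longest in AE period |
|---|---|---|---|---|---|
| 20 Mar | missing | 20 Mar | 1 | 1 | 45 |
| 28 Mar | missing | 28 Mar | 1 | 1 | 37 |
| 28 Mar | MAR2014 | 28 Mar | 1 | 1 | 4 |
| 28 Mar | APR2014 | 1 Apr | 5 | 5 | 34 |
| 5 Apr | missing | 5 Apr | 1 | 1 | 29 |
| 5 Apr | APR2014 | 5 Apr | 1 | 1 | 26 |
| 5 Apr | 2014 | 5 Apr | 1 | 1 | 29 |
| 10 Mar | APR2014 | 1 Apr | 23 | 23 | 52 |
| 10 Mar | missing | 20 Mar | 11 | 1 | 55 |
| 10 Mar | 2014 | 20 Mar | 11 | 1 | 55 |
| 10 Mar | MAR2014 | 20 Mar | 11 | 1 | 22 |

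- The seven events with onset on or after the last dose get the shortest duration. So does the one with earlier onset and a stop month wholly after the last dose.
- The other three are cut at the last dose. They are short of the longest duration but are not the shortest.
- With the cap moved to 3 May, all 11 equal the last column.

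**Prevalence.** Assumed dates: Day 1 = 15 Jan 2013, last dose 10 Jan 2014 (Day 361), PEG-J removal 17 Jan 2014 (Day 368), AE onset 20 Dec 2013 (Day 340), stop date missing.

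- Imputed stop = max{10 Jan 2014, 01JAN1000, 20 Dec 2013} = 10 Jan 2014, Day 361.
- Treatment Period End Day = 368 + 30 = 398.
- Year 2 is Days 366 to 730 (SAP Table 3). Since 398 ≥ 366, the subject is in the Year 2 denominator. Since 361 < 366, the event is not in the numerator.
- With the cap moved, the stop is Day 398 and the event counts.

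**How often a boundary falls in the gap.** Let w be the days from last infusion to PEG-J removal. A boundary lies between the last dose and the period end for 30 + w of the 365 possible last-dose days in a year. If exit timing is uniform over the year, the chance is (30 + w)/365:

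- w = 0: 30/365 = 8.2%
- w = 7: 37/365 = 10.1%
- w = 30: 60/365 = 16.4%

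Table 3 has a single open interval after Day 1825, so the chance is 0 when the last dose is after that day.

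**Outputs that use the stop date.** TEAE status and by-year incidence depend on the start date only. By-year prevalence (AET014) is planned as Tables `14.3__1.2.1.9`, `14.3__1.2.2.6` and `14.3__1.2.2.11`. AEL001 prints original dates, but its relative days may rest on imputed ones.

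**The case against.** The reach is narrow, and most of that argument stands. Ongoing events are not imputed, data are checked before lock, and protocol 12.1.1 reserves an unknown outcome for loss to follow-up. A missing stop date without the ongoing flag should therefore be uncommon. For subjects still on treatment at the 2015 interim, last infusion and last PEG-J exposure both equal the Cutoff Date, so the gap concerns subjects who have stopped.

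A reader might infer more than the documents support:

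- *That every event around stopping gets the shortest duration.* It does not; the last three rows of the table are truncated but not minimal.
- *That AE incidence or reported AE durations are wrong.* Incidence does not use the stop date, and no table summarises AE duration.
- *That 8% to 16% of events are lost.* The percentage is the chance that a boundary falls in the gap, and it matters only for AEs with an incomplete stop date. Even for those it is an upper bound. A known stop month narrows the window, an onset after the last dose shortens it, and an event that starts in the new year is counted anyway.
- *That the recorded relative stop days are known to be too early.* The true dates are unknown. They are early only relative to the SAP's own longest-duration principle.

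It is also fair that simply moving the cap to PEG-J + 30 days is not enough. It could carry an event past a subject's death. A partial stop date wholly after the new cap would still be set to its earliest possible date.

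**Conclusion.** The point holds as a minor internal contradiction. The stop-date rule uses the last drug date where the stated principle, the AE Treatment Period and the prevalence denominator all call for last PEG-J exposure + 30 days. Relative to that principle, the three AET014 tables can only be understated.

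The size cannot be fixed from the documents. It is at most about (30 + w)/365 per affected AE, assuming uniform exit timing and a last dose no later than Day 1825, applied to a number of incomplete stop dates that is unknown and probably small. It is worth correcting because the change is cheap, not because it threatens a main safety conclusion.

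**What to change.** In the stop-date rule of SAP 8.5.1, replace the last-administration date in the first candidate with the earliest of:

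- the Date of the Last 3005 PEG-J Exposure (RFENDT2N) + 30 days;
- the date of death;
- for the interim analysis only, the Cutoff Date.

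Reword the stated property as the longest duration within the AE Treatment Period. That also covers partial stop dates lying wholly after the period: the event then spans the rest of the period whichever day is imputed. Leave the start-date rule unchanged.

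The cost is a reworded rule and a small change to one derivation. No new data collection is needed, and incidence tables do not change. The denominator has no bound at death or at the Cutoff Date, so a subject who died, or who was still on treatment at the interim, may still be counted in a year that the imputed stop date does not reach. That comes from the denominator definition, and a footnote to AET014 would be enough.
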